7.2.2 SAE reporting

To ensure patient safety, every SAE, regardless of causality, occurring after the patient has provided informed consent and until 30 days following the last administration of study treatment must be reported to Novartis safety within 24 hours of learning of its occurrence. Any SAEs experienced after the 30 day period after the last study visit should only be reported to Novartis safety if the investigator suspects a causal relationship to study treatment. For patients who sign the pre-screening informed consent form, SAEs which occur after signature of this consent will only be captured if they are reported to be causally related with study procedures (i.e. blood sampling).

All follow-up information for the SAE including information on complications, progression of the initial SAE and recurrent episodes must be reported as follow-up to the original episode within 24 hours of the investigator receiving the follow-up information. An SAE occurring at a different time interval or otherwise considered completely unrelated to a previously reported one must be reported separately as a new event.

Information about all SAEs is collected and recorded on the Serious Adverse Event Report Form; all applicable sections of the form must be completed in order to provide a clinically thorough report. The investigator must assess the relationship of each SAE to each specific component of study treatment, (if study treatment consists of several components) complete the SAE Report Form in English, and submit the completed form within 24 hours to Novartis. Detailed instructions regarding the submission process and requirements for signature are to be found in the investigator folder provided to each site.

Follow-up information is submitted as instructed in the investigator folder. Each re-occurrence, complication, or progression of the original event must be reported as a follow-up to that event regardless of when it occurs. The follow-up information should describe whether the event has resolved or continues, if and how it was treated, whether the blind was broken or not, and whether the patient continued or withdrew from study participation.

If the SAE is not previously documented in the Investigator's Brochure or Package Insert and is thought to be related to the study treatment a Patient Safety associate may urgently require further information from the investigator for health authority reporting. Novartis may need to issue an Investigator Notification (IN) to inform all investigators involved in any study with the same study treatment that this SAE has been reported. Suspected Unexpected Serious Adverse Reactions (SUSARs) will be collected and reported to the competent authorities and relevant

ethics committees in accordance with EU Guidance 2011/C 172/01 or as per national regulatory requirements in participating countries.

Note: SAEs must be reported to Novartis within 24 hours of the investigator learning of its occurrence/receiving follow-up information.

7.3 Liver safety monitoring

To ensure patient safety and enhance reliability in determining the hepatotoxic potential of an investigational drug, a process for identification, monitoring and evaluation of liver events has to be followed. For this study in patients likely to have altered liver function at baseline, an adapted monitoring process will be followed.

Subjects who develop elevations in liver-related laboratory parameters and/or clinical symptoms suggestive of liver disease should be managed according to [Table 14-1](#). If ALP, ALT, AST, or bilirubin elevations reach the specified thresholds outlined in [Table 14-1](#), the subject must return to the study site for re-evaluation within 48 to 72 hours after the laboratory results becoming available, at which time central confirmatory laboratory testing will be performed. This includes ALP, ALT, AST, total and direct bilirubin and INR. Central laboratory values for INR that are greater than 1.5 should also be repeated in the local laboratory in addition to the central laboratory. At the same time repeat clinical laboratory samples are drawn, [REDACTED]

[REDACTED] If prompt evaluation is not possible within 48 to 72 hours following receipt of abnormal laboratory results, study drug should be interrupted immediately (date of last study drug dose must be recorded in the eCRF) and the subject must return to the study site as soon as possible for re-evaluation. The sponsor should be notified of laboratory abnormalities and any clinical symptoms within 48 hours of available laboratory results and/or assessment of clinical symptoms.

If the elevation is confirmed, close observation of the patient will be initiated, including consideration of treatment interruption or discontinuation (as described in [Table 14-1](#)) if deemed appropriate and close monitoring, causality and clinical evaluation should be performed as below;

- Repeating the liver tests to confirm elevation as described in [Table 14-1](#)
- Discontinuation of the investigational drug if appropriate. Note that discontinuation is mandatory in the case of decompensated cirrhosis as defined by ascites, bleeding esophageal varices, hepatic encephalopathy, jaundice or any other liver decompensation related symptom
- Hospitalization of the patient if appropriate
- An investigation of the liver event which needs to be followed until resolution
- Obtain a more detailed history of symptoms and prior or concomitant diseases
- Obtain a history of concomitant drug use (including nonprescription or over-the-counter medications and herbal and dietary supplement preparations), alcohol use, recreational drug use, and special diets

- Rule out acute viral hepatitis Types A, B, C, D, and alcoholic hepatitis; hypoxic/ischemic hepatopathy; autoimmune hepatitis and biliary tract disease
- Obtain a history of exposure to environmental chemical agents

These investigations can include serology tests, liver biopsy, imaging and pathology assessments, hepatologist's consultancy, based on investigator's discretion.

Any cases of possible drug-related liver injury will be blindly adjudicated by a hepatologist with expertise in drug-related liver injury and as necessary reviewed by the DMC which includes additional hepatologists.

Subjects who permanently discontinue study drug due to potential liver toxicity must be followed for close monitoring until abnormalities stabilize to baseline levels or baseline grade of abnormality and the subject is asymptomatic. All follow-up information, and the procedures performed must be recorded on the appropriate CRFs.

7.4 Renal safety monitoring

The following two categories of abnormal renal laboratory values have to be considered during the course of the study:

- Serum event:
 - confirmed (after ≥ 24 h) increase in serum creatinine of $\geq 25\%$ compared to baseline during normal hydration status
- Urine event
 - new onset ($\geq 1+$) proteinuria;
 - new onset ($\geq 1+$), hematuria or glycosuria

Every renal laboratory trigger or renal event as defined in [Table 15-1](#) in [Appendix 3](#) should be followed up by the investigator or designated personnel at the trial site as summarized in [Appendix 3](#).

7.5 Reporting of study treatment errors including misuse/abuse

Medication errors are unintentional errors in the prescribing, dispensing, administration or monitoring of a medicine while under the control of a healthcare professional, patient or consumer (European Medicines Agency definition).

Misuse refers to situations where the medicinal product is intentionally and inappropriately used not in accordance with the protocol.

Abuse corresponds to the persistent or sporadic, intentional excessive use of a medicinal product, which is accompanied by harmful physical or psychological effects.

Study treatment errors and uses outside of what is foreseen in the protocol will be collected in the appropriate CRF, irrespective of whether or not associated with an AE/SAE and reported to Safety only if associated with an SAE. Misuse or abuse will be collected and reported in the safety database irrespective of it being associated with an AE/SAE.

Table 7-1 Guidance for capturing the study treatment errors including misuse/abuse

Treatment error type	Document in CRF (Yes/No)	Document in eCRF capturing AE	Complete SAE form
Unintentional study treatment error	Yes	Only if associated with an AE	Only if associated with an SAE
Misuse/Abuse	Yes	Yes,	Yes, even if not associated with a SAE

7.6 Pregnancy reporting

To ensure patient safety, any pregnancy occurring in a study subject or their partner after signing the informed consent must be reported to Novartis within 24 hours of learning of its occurrence. The pregnancy should be followed up to determine outcome, including spontaneous or voluntary termination, details of the birth, and the presence or absence of any birth defects, congenital abnormalities, or maternal and/or newborn complications.

Pregnancy must be recorded on the Pharmacovigilance Pregnancy Form and reported by the investigator to the local Novartis Patient Safety department. Pregnancy follow-up should be recorded on the same form and should include an assessment of the possible relationship to the study treatment.

Any SAE experienced during the pregnancy and unrelated to the pregnancy must be reported on a SAE form.

Pregnancy outcomes should be collected for the female partners of any males who took study treatment in this study. Consent to report information regarding these pregnancy outcomes should be obtained from the female partner.

8 Data review and database management

8.1 Site monitoring

Before study initiation, at a site initiation visit or at an investigator's meeting, a Novartis representative will review the protocol and data capture requirements (eCRFs) with the investigators and their staff. During the study, Novartis employs several methods of ensuring protocol and GCP compliance and the quality/integrity of the sites' data. The field monitor will visit the site to check the completeness of patient records, the accuracy of data capture / data entry, the adherence to the protocol and to Good Clinical Practice, the progress of enrollment, and to ensure that study treatment is being stored, dispensed, and accounted for according to specifications. Key study personnel must be available to assist the field monitor during these visits. Continuous remote monitoring of each site's data may be performed by a centralized Novartis CRA organization. Additionally, a central analytics organization may analyze data & identify risks & trends for site operational parameters, and provide reports to Novartis Clinical Teams to assist with trial oversight.

The investigator must maintain source documents for each patient in the study, consisting of case and visit notes (hospital or clinic medical records) containing demographic and medical information, laboratory data, electrocardiograms, and the results of any other tests or

assessments. All information on eCRFs must be traceable to these source documents in the patient's file. Data not requiring a separate written record will be defined before study start and will be recorded directly on the eCRFs. The investigator must also keep the original informed consent form signed by the patient (a signed copy is given to the patient).

The investigator must give the monitor access to all relevant source documents to confirm their consistency with the data capture and/or data entry. Novartis monitoring standards require full verification for the presence of informed consent, adherence to the inclusion/exclusion criteria, documentation of SAEs, and of data that will be used for all primary variables. Additional checks of the consistency of the source data with the eCRFs are performed according to the study-specific monitoring plan. No information in source documents about the identity of the patients/subjects will be disclosed.

8.2 Data collection

Designated investigator staff will enter the data required by the protocol into the Electronic Case Report Forms (eCRFs) using fully validated secure web-enabled software that conforms to US CFR 21 Part 11 requirements. Designated investigator site staff will not be given access to the system until they have been trained.

Automatic validation procedures within the system check for data discrepancies during and after data entry and, by generating appropriate error messages, allow the data to be confirmed or corrected online by the designated investigator site staff. The Investigator must certify that the data entered into the electronic Case Report Forms are complete and accurate. After database lock, the investigator will receive copies of the patient data for archiving at the investigational site.

8.3 Database management and quality control

Novartis personnel (or designated CRO) will review the data entered by investigational staff for completeness and accuracy. Electronic data queries stating the nature of the problem and requesting clarification will be created for discrepancies and missing values and sent to the investigational site via the EDC system. Designated investigator site staff is required to respond promptly to queries and to make any necessary changes to the data.

Concomitant medications entered into the database will be coded using the World Health Organization (WHO) Drug Reference List, which employs the Anatomical Therapeutic Chemical classification system. Concomitant procedures, non-drug therapies and adverse events will be coded using the Medical dictionary for regulatory activities (MedDRA) terminology.

Laboratory samples will be processed centrally and the results will be sent electronically to Novartis (or a designated CRO).

ECG readings will be processed centrally and the results will be sent electronically to Novartis (or a designated CRO).

[REDACTED]

[REDACTED]

[REDACTED]

Biopsy results will be read centrally and the results will be sent electronically to Novartis (or a designated CRO).

Randomization codes and data about all study drug(s) dispensed to the patient and all dosage changes will be tracked using an Interactive Response Technology (IRT). The system will be supplied by a vendor, who will also manage the database. The data will be sent electronically to Novartis (or a designated CRO).

Each occurrence of a code break via IRT will be reported to the clinical team and monitor. The code break functionality will remain available until study shut down or upon request of Novartis. The occurrence of relevant protocol deviations will be determined. After these actions have been completed and the database has been declared to be complete and accurate, it will be locked and the treatment codes will be unblinded and made available for data analysis. Any changes to the database after that time can only be made after written agreement by Novartis Development management.

[REDACTED]

8.4 Data Monitoring Committee

This study will use the tropifexor program level external DMC. The committee will consist of at least two physicians and a statistician who are not otherwise associated with the study, and who are experienced in multicenter trials in hepatology and general medicine. The main tasks of the Committee for this study will be to review emerging safety data and primary efficacy data and provide recommendations to the Sponsor concerning safety.

The program Data Monitoring Committee Charter provides detail on the committee composition and processes.

The DMC will review safety, including AEs and laboratory parameters, on a regular basis. In addition, in the event that more than 3 patients develop similar SAEs, the DMC chairman will be alerted. Further details regarding relevant data and actions will be specified in the separate DMC charter.

8.5 Adjudication Committee

Any cases of possible drug-related liver injury will be blindly adjudicated by a hepatologist with expertise in drug-related liver injury and as necessary reviewed by the DMC which includes additional hepatologists.

[REDACTED]

9 Data analysis

The final (end-of study) analysis will be conducted on all patient data collected up to the Week 52 visit.

The analysis will be conducted on all subject data at the time the trial ends. Any data analysis carried out independently by the investigator should be submitted to Novartis before publication or presentation.

9.1 Analysis sets

- Screened set (SCR) – All patients who signed the informed consent.
- Randomized set (RAN) – All patients who received a randomization number, regardless of receiving trial medication.
- Full analysis set (FAS) – All patients to whom study treatment has been assigned*. Following the intent-to-treat (ITT) principle, patients are analyzed according to the treatment they have been assigned to at randomization.
- Safety set (SAF) - All patients who received at least one dose of study drug and have at least one post-baseline safety assessment. Of note, the statement that a patient had no adverse events also constitutes a safety assessment. Patients will be analyzed according to the treatment received.

*excluding patients who were mis-randomized and did not take investigational drug. Mis-randomized patients are those who were not qualified for randomization, but were inadvertently randomized into the study.

The number of patients in each analysis set will be presented by treatment group and overall for the screened set.

9.2 Patient demographics and other baseline characteristics

Demographic variables and other baseline characteristics will be summarized for the FAS. Descriptive statistics (mean, median, standard deviation, minimum and maximum) will be presented for continuous variables for each treatment group and for all patients (total). The number and percentage of patients in each category will be presented for categorical variables for each treatment group and all patients (total). In addition, all relevant medical history, and protocol solicited medical history will be summarized by treatment group.

9.3 Treatments

The duration of investigational treatment exposure (days) will be summarized by treatment group for the SAF, both descriptively (i.e. mean, standard deviation, median, quartiles, minimum and maximum) and by duration category (e.g. weeks).

The proportion of patients with dose reduction will be presented by treatment group.

Medications will be identified using the WHO dictionary including ATC code and presented for the SAF. Prior medications are defined as any medications taken prior to the randomization visit (regardless of whether they are stopped or continued after randomization). Concomitant medications and significant non-drug therapies are defined as those used during the double-

blind period. Prior and concomitant medications will be summarized by treatment group in separate tables. Medications will be presented in alphabetical order, by ATC codes and grouped by anatomical main group (the first level of the ATC code). Tables will also show the overall number and percentage of subjects receiving at least one drug of a particular ATC code and at least one drug in a particular anatomical main group.

Concomitant medications that were prohibited as per protocol and given during the conduct of the study as well as significant non-drug therapies will be provided in separate tables.

9.4 Analysis of the primary variable(s)

9.4.1 Primary Variable(s)

Safety (to be assessed in SAF):

- Occurrence of adverse events
- Occurrence of serious adverse events
- Occurrence of adverse events resulting in permanent discontinuation
- Occurrence of adverse events of special interest
- Changes in Vital signs
- Changes in Laboratory data

9.4.2 Statistical model, hypothesis, and method of analysis

There are no pre-specified hypotheses and statistical models in this study. The methods to analyze the primary safety variables are outlined in [Table 9-1](#).

Table 9-1 Primary variables and methods of analysis

Variable	Method of analysis
Occurrence of adverse events	Summary table of absolute and relative frequency, overall and by preferred term
Occurrence of serious adverse events	Summary table of absolute and relative frequency, overall and by preferred term
Occurrence of adverse events resulting in discontinuation or dose reduction of study treatment	Summary table of absolute and relative frequency, overall and by preferred term
Occurrence of adverse events of special interest	Summary table of absolute and relative frequency, overall and by type of AE as the risks are described for both tropifexor and CVC (risk definition for tropifexor are those that appear in in tropifexor and CVC IB)
Changes in vital signs	Descriptive statistics by visit
Changes in Laboratory data	Descriptive statistics by visit

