Study Treatment Discontinuation (TD)	When the patient permanently stops taking study treatment prior to the defined study treatment completion date.
Variable	A measured value or assessed response that is determined in specific assessments and used in data analysis to evaluate the drug being tested in the study.
Withdrawal of study consent (WoC)	Withdrawal of consent from the study occurs only when a subject does not want to participate in the study any longer, and does not allow any further collection of personal data.

Amendment 3

Amendment rationale

The conduct of clinical trials has been impacted by the COVID-19 pandemic and related measures including national government mandates, closures of local hospitals and research facilities, reassignment of research personnel, patient travel restrictions and delays in the shipment of study treatment and trial supplies.

The purpose of this amendment is to implement a plan for treatment continuity, patient safety monitoring and maintaining the integrity of the trial. The implemented measures are only for the period of the COVID-19 pandemic, and standard visit schedule and assessments as outlined in [Table 6-1](#) should resume as soon as patients are able to visit study sites and undergo all end of treatment assessments

At the time of amendment (V03) release, enrollment is completed with 193 patients randomized.

Changes to the protocol

This amendment provides the option to extend the study treatment for patients who are unable to come to site for the week 48 visit as scheduled due to COVID-19 pandemic restrictions.

The changes to specific sections of the protocol are as below:

- Section 3.6: Updated to clarify the possible benefits and risks of longer study treatment
- Section 5.5.2: updated to include the stepwise approach to extend study treatment for patients who are unable to come to the study site for their Week-48, End of treatment (EOT) visit as scheduled per study protocol due to COVID-19 pandemic related restrictions
- Section 6 and table 6.1: updated to include remote consultation for patients who are unable to come to the study site for their study visits (except week-48, End of treatment visit) as scheduled per study protocol due to COVID-19 pandemic related restrictions. The footnotes revised to clarify the instructions for urine pregnancy test and study treatment extension.

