The tropifexor + CVC drug-drug interaction study CLJC242A2101 in healthy subjects suggested that co-administration of CVC reduces tropifexor exposure (both C_{max} and AUC 0-24h) by about 35%. No safety concerns were identified at the doses of 60 µg tropifexor alone, 150 mg CVC alone or their combination, administered once daily with a standard breakfast for 14 days. In addition, an across-study exploratory comparison indicated that tropifexor plasma exposure (both C_{max} and AUC) at 60 µg administered fasted (study CLJN452X2101) is similar to that at the same dose administered following a standard breakfast (study CLJC242A2101).

In summary, as compared to the fasted status, a high-fat meal increases tropifexor exposure but a standard meal appears not to. It is recommended that NASH patients, in this study, will be dosed following a standard meal without high fat (i.e. per AHA diet see [appendix 17](#)).

Tropifexor and cenicriviroc (combination) - safety considerations

In the DDI study (CLJC242A2101) the safety and tolerability of the combination treatment of tropifexor + CVC were found to be comparable to those of each of the mono therapy treatment. No additional particular safety considerations are expected for the combination of tropifexor and cenicriviroc, beyond those previously observed for each of the individual monotherapies (see [section 1.1](#) and [section 3.6](#) for risks). As both drugs may increase liver transaminases, there is a potential for an additive effect, thus close liver monitoring is included. Diarrhea has been identified as a non-serious adverse effect for cenicriviroc and is a possible (but unconfirmed) adverse effect of tropifexor from animal studies.

Tropifexor and cenicriviroc (combination) - rationale

Due to the multifactorial etiology of NAFLD/NASH and limited monotherapy results so far, the combination therapy of compounds with different mechanisms of actions may provide more effective therapy for NASH patients.

This study will combine the potent FXR agonist (anti-steatotic, anti-inflammatory and anti-fibrotic) tropifexor and the CCR2/5 inhibitor (anti-inflammatory and anti-fibrotic) cenicriviroc. The preclinical animal study STAM mouse models of diet induced NASH, shows that combination therapy of tropifexor and cenicriviroc have additive effects on steatosis, ballooning, and inflammation.

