5.5.5 Permitted dose adjustments and interruptions of study treatment

For potential drug-related adverse events, temporary interruptions are permitted up to 28 consecutive days. Study drugs can be reintroduced under careful monitoring if the investigator feels it is in the best interest of the patient. Interruption of study drug for more than 28 consecutive days should lead to permanent discontinuation of the patient from study drug with the respective follow-up visits.

Investigational treatment dose adjustments are not permitted.

These changes must be recorded on the appropriate eCRF.

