5.6.2 Discontinuation of study treatment

Discontinuation of study treatment for a patient occurs when study drug is stopped earlier than the protocol planned duration, and can be initiated by either the patient or the investigator. The investigator must discontinue study treatment for a given patient if, on balance, he/she believes that continuation would negatively impact the risk/benefit of trial participation.

Study treatment must be discontinued under the following circumstances:

- Patient wish
- Pregnancy (Ref. protocol [Section 6.5.6](#) and [Section 7.6](#))
- Use of prohibited treatment as per recommendations ([Section 5.5.8](#))
- Any situation in which study participation might result in a safety risk to the patient
- Emergence of the following adverse events:
 - Hypersensitivity reaction to tropifexor or CVC
 - For ALT, AST, total bilirubin and/or alkaline phosphatase elevations mandating study treatment discontinuations ([Section 7.3](#) and [Table 14-1](#) for further instructions and monitoring).
 - Specified renal events ([Section 7.4](#) and [Table 15-1](#) for further instructions and monitoring).
 - Other SAE that are related to study drug.
 - Other life-threatening SAE regardless of attribution to study drug.
 - Any other adverse events, abnormal laboratory values or abnormal test result that indicate a safety risk to the patient.
 - Decompensated cirrhosis as defined by ascites, bleeding esophageal varices, hepatic encephalopathy, jaundice or any other liver decompensation related symptom.

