6.3 Treatment exposure and compliance

[figure not shown]
All doses of study treatment administration will be recorded on the appropriate CRF page. Compliance will be assessed by means of site and subject-specific drug accountability by Novartis study personnel during the site monitoring visits using medication pack numbers, Drug Label Form information and information collected by IRT.

[figure not shown]

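### The safety tables pair AE-related discontinuation with dose reduction, which the protocol forbids; interruption with restart, which it allows, is counted in no visible planned summary

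*Protocol*

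**What the plan says.** The treatment-action row among the primary safety variables, in protocol Table 9-1 and again in SAP Table 2-1, is "Occurrence of adverse events resulting in discontinuation or dose reduction of study treatment". Protocol 9.3 adds a proportion of patients with dose reduction, by arm.

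The dosing rules are in protocol 5.5.5. On reduction: "Investigational treatment dose adjustments are not permitted". On interruption: "For potential drug-related adverse events, temporary interruptions are permitted up to 28 consecutive days". On restart: "Study drugs can be reintroduced under careful monitoring if the investigator feels it is in the best interest of the patient". An interruption longer than 28 consecutive days leads to permanent discontinuation.

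Elsewhere the variable covers discontinuation only. Protocol 9.4.1 specifies permanent discontinuation, and the AE lists in protocol 9.5.2.1 and SAP 2.8.1 name discontinuation alone. The protocol glossary defines study treatment discontinuation as "When the patient permanently stops taking study treatment prior to the defined study treatment completion date". A patient who interrupts and resumes does not meet that definition.

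**The concern.** The tables name an action that the protocol rules out and omit the one it allows. With reduction barred, interruption is the only permitted dosing response short of stopping, and tolerability of the combination against each monotherapy is the primary objective.

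Take a patient whose diarrhea halts dosing for two weeks and who then resumes. The event appears by preferred term, severity and relatedness, but no row shows that dosing stopped. Two arms could differ in how often this happens and look the same on the treatment-action row. The example is relevant but should not be pressed. Protocol 1.1 says "Diarrhea has been identified as a non-serious adverse effect for cenicriviroc"; for tropifexor it calls the effect only possible and unconfirmed, on the basis of animal studies.

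**Working it through.** The plan gives no figure to reproduce. The check compares the dosing rules with every visible safety and exposure summary, then sizes what is left.

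**1. Can the dose-reduction items fill?** Protocol 5.5.5 bars adjustments, and protocol Table 5-1 gives one fixed regimen per arm with no lower step. Protocol 3.6 does mention reducing the dose if necessary, but that is general risk text and 5.5.5 is the operative rule. Because 140 µg is taken as three capsules (10 + 30 + 100 µg) from separate bottles, a lower dose can still occur by error or deviation. Apart from that, the row equals the count of permanent discontinuations and the 9.3 proportion is zero.

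**2. How prominent is interruption in the rules?** The action rows of protocol Table 14-1:

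| Action | Rows |
|---|---|
| Interrupt | 12 |
| Continue | 4 |
| Permanently discontinue | 2 |
| Continue or interrupt | 1 |
| Total | 19 |

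Of the 12 interrupt rows, 4 require symptoms, 5 require a concurrent bilirubin or INR criterion, and 3 are bilirubin alone. These are shares of rows, not of events. Protocol Table 15-1 also lists interruption as an option for some renal events.

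**3. Which interruptions escape the discontinuation count?**
- Liver: Table 14-1, footnote e, allows restart only if values have resolved, the interruption lasted under 28 days and the deterioration was not considered drug-related. Recurrence after restart is a permanent stop. What escapes is the short, resumed interruption judged unrelated.
- Other AEs: protocol 5.6.2 requires a stop for "Other SAE that are related to study drug", for life-threatening SAEs regardless of cause, and for any other AE or abnormal result indicating a safety risk. What escapes is the non-serious, non-liver AE not judged a safety risk, interrupted and resumed. Here 5.5.5 sets no relatedness bar to restart; it is written for potentially drug-related events and leaves restart to the investigator.

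**4. Does another visible summary catch them?**
- Liver events: SAP 2.8.1 and 5.3.1 count Table 14-1 events on laboratory criteria alone. In 5 + 3 = 8 of the 12 interrupt rows the action applies with or without symptoms, so the table shows who met those triggers. The 4 symptom rows cannot be separated. The table disregards confirmation, on which the Table 14-1 actions rest, and does not record whether dosing was halted.
- Exposure: SAP 2.4.1 takes last dose date minus first dose date plus 1, so interruption days count as exposure.

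**5. Size.** Interruption rates are assumed, with 50 patients per arm:
- 2%: 0.02 × 50 = 1 patient
- 5%: 0.05 × 50 = 2.5 patients
- 10%: 0.10 × 50 = 5 patients

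Exposure for one patient finishing week 48, a planned 48 × 7 = 336 days:
- 14-day interruption: 336 − 14 = 322 days; 322 / 7 = 46.0 weeks
- 28-day interruption: 336 − 28 = 308 days; 308 / 7 = 44.0 weeks

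Net of the gap, both belong in the category from 36 to under 48 weeks. The SAP formula gives 336 / 7 = 48 weeks and places them in 48 to under 52. At arm level the effect is small: with 10% of patients interrupted for 28 days, mean exposure is overstated by 0.10 × 28 / 336 = 0.8% of the planned course.

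**The case against.** The strongest reply is that the wording distorts no result. The row is a union, so with no reductions it equals the discontinuation count, which is what the defined variable asks for. SAP 2.4.1 does not carry the 9.3 dose-reduction summary forward. The analysis is descriptive, tests no hypothesis, and judges the whole safety profile. All of this stands, and it keeps the point modest. It does not put interruptions into any table.

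The likely numbers are also small. Protocol 1.1 reports drug-related diarrhea of at least Grade 2 in 2.1% of CVC patients over one year of the earlier phase 2b trial, or 0.021 × 50 = about 1 patient per arm. AE severity is itself graded by interference with normal activities, so the AE tables carry part of the tolerability signal.

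Absence cannot be proved either. The SAP refers to separate table shells and an internal liver-safety analysis plan, neither public, and parts of the SAP are redacted. The claim is therefore limited to visible summaries.

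Three stronger readings are tempting and are not supported:
- A reader might infer from 5.5.5 that the dose-reduction items must be empty. Protocol 3.6 conflicts with 5.5.5, and capsule errors are possible.
- A reader might infer from 12 of 19 rows that most liver triggers go unreported. The laboratory triggers in 8 of those 12 rows are already tabulated, and drug-related, long or recurrent liver interruptions should become counted discontinuations.
- A reader might infer that the exposure summaries are materially wrong. The formula is stated openly, and the arm-level effect is 0.8% even in the 10% example.

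**Conclusion.** The point holds in limited form. The treatment-action row of a primary tolerability variable names a forbidden action, and the permitted one, interruption with restart, appears in no visible planned summary. What is missing is how often AEs halted dosing without ending it, within the two groups identified above.

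The size is 1 to 5 patients per arm of 50 at assumed rates of 2% to 10%; the documents support no particular rate. The conclusion rests on 5.5.5 prevailing over the general text in 3.6, on the stopping rules in 5.6.2 and Table 14-1 being followed, and on the non-public shells and liver-safety plan holding no interruption table. If they do hold one, only a wording error remains.

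**What to change.** In SAP Table 2-1 and SAP 2.8.1, replace dose reduction with temporary interruption. Report, by arm and preferred term, AEs leading to permanent discontinuation and, separately, AEs leading to temporary interruption, and give the number of patients interrupted. List any dose reduction that occurs as a dosing error or protocol deviation, so that removing the category loses no information. Align protocol Table 9-1 and 9.3 at the next amendment; under protocol 11.1 this wording alone does not justify a separate one. Exposure net of interruption days is optional. The stopping rules need no change.

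The cost is one or two descriptive tables before database lock, with no new data collection. Protocol 6.3 states "All doses of study treatment administration will be recorded on the appropriate CRF page", 5.5.5 requires these changes to be recorded on the eCRF, and 7.1 records the action taken on study treatment for each AE. If the shells already contain the tables, the cost is the wording correction alone.
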